#### **2.3.2.3. Drug relatedness**

Proportion of participants experiencing at least one TEAE related to any study medication. A related AE is defined as 'Possibly', 'Probably', or 'Certainly' related to study medication.

#### **2.3.2.4. Seriousness**

Proportion of participants experiencing at least one serious TEAE. A serious AE (SAE) is defined as any untoward medical occurrence that at any dose results in death, is life-threatening, is a congenital anomaly/birth defect, requires in-participant hospitalisation or prolongation, results in significant disability/incapacity, or is a medically important event.

#### **2.3.2.5. Leading to treatment discontinuation**

Proportion of participants experiencing a TEAE that lead to treatment discontinuation. This will be AEs where action taken with study treatment is 'Permanently Discontinued' for BPaMZ or HRZE/HR.

#### **2.3.2.6. Leading to study discontinuation**

Proportion of participants experiencing a TEAE that lead to study discontinuation. This will be AEs where action taken with study treatment is 'Withdrawn from Study'.

#### **2.3.2.7. Leading to death**

Proportion of participants experiencing a TEAE that lead to death. This will be AEs where the answer to 'Outcome' on the AE form is 'Fatal'.

#### **2.3.2.8. Liver-related, drug and liver-related and serious liver-related TEAEs**

The proportion of participants experiencing liver related, drug and liver related and serious liver related TEAEs. Liver related AEs are those where the preferred term specifies 'Hepatic' Drug and liver related are those AEs that are liver related and related to a drug and serious liver related TEAEs are those that are liver related and the AE is considered serious (as described in § 2.3.2.4).

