### **8.2.8. Liver-related TEAE**

A summary of TEAEs that has preferred terms under “Hepatic disorders” according to MedDRA dictionary will be presented by SOC and PT in the same manner to that described in §8.2.1. In addition, any liver-related TEAE tables will be presented by region, sex, age (< vs. >median), previous alcohol intake and HIV status.

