#### **8.2.8.1. Liver and drug-related TEAEs**

A summary of liver-related TEAEs that are drug related (i.e. ‘Possibly’, ‘Probably’, and ‘Certainly’) will be presented by SOC and PT for treatment arm and drug in the same manner to that described in §8.2.1.

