#### **8.2.8.3. Incidence of hepatotoxicity**

Proportion of participants experiencing at least one liver function test (LFT; AST or ALT) that is  $\geq 3$  x ULN or at least one hepatic SAE (as described in §8.2.8). This will be summarised in a table by treatment arm (and combining the BPaMZ arms to give a BPaMZ total). In addition we will summarise for those who have had a hepatotoxicity what their hepatitis status (A, B and C) was at baseline, at the time of the event and the change from baseline to time of event.

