## NtF2 Reporting of TEAEs under SMQs

This note to file clarifies the reporting of TEAEs under the SMQs.

The SimpliciTB SAP v3.0 (dated May 2021) section 8.2.9 states:

*"The number and percentage of participants with the following specific TEAEs will be presented separately: grade 2, 3 or 4 myalgia, grade 3 or 4 cardiac rhythm disturbances, grade 3 or 4 lipase, pancreatitis, peripheral neuropathy and myelosuppression."*

Section 8.2.9 should have said:

"The number and percentage of participants with the following specific TEAEs will be presented separately: grade 2, 3 or 4 myalgia, grade 3 or 4 cardiac rhythm disturbances, pancreatitis, peripheral neuropathy and myelosuppression."

In addition, the following should have been included in the SAP:

"Following an SMQ analysis of the adverse events using the online MedDRA SMQ Analysis tool, the number and percentage of participants with TEAEs falling under the following SMQs will be presented":

SMQ Category	SMQ Analysis Rule
Hepatic Event	All PTs under SMQ (hepatic disorder)
Seizure (neurological)	All PTs under SMQ (Convulsions)
Peripheral Neuropathy	All PTs under SMQ (peripheral neuropathy)
Lactic Acidosis	All PTs under SMQ (lactic acidosis)
Pancreatitis, Amylase elevation, Lipase elevation	All Narrow PTs and broad B terms under acute pancreatitis SMQ
Optic neuropathy	All PTs under SMQ (optic nerve disorder)
Myelosuppression	All PTs under SMQ (Haematopoetic cytopenias)
Cardiac Rhythm Disturbances	All PTs under SMQ (Cardiac arrhythmias)
Musculoskeletal System (Myalgia)	All PTs under SMQ (Rhabdomyolysis/myopathy), excluding the following PTs: Creatinine renal clearance decreased Hypocalcaemia

Signed

Date: 11th November 2021

[name]  
Statistician for the SimpliciTB trial  
Institute of Clinical Trials and Methodology  
MRC Clinical Trials Unit at UCL  
[name]  
[name]

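### Section 2.3.2.8 defines liver-related events by the word 'Hepatic' in the preferred term, which conflicts with section 8.2.8 and, applied literally, would under-count three named safety outcomes

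*SAP*

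**What the plan says.** Three places in the SAP say which adverse events count as hepatic.

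- **Section 2.3.2.8**, among the secondary safety outcomes: "Liver related AEs are those where the preferred term specifies" 'Hepatic'. The same paragraph forms the drug-related and serious liver outcomes as subsets of the events so defined.
- **Section 8.2.8**, which specifies the table, takes preferred terms under 'Hepatic disorders', "according to MedDRA dictionary will be presented by SOC and PT". It does not say whether this is an SMQ or a level of the MedDRA hierarchy.
- **Note to File 2** sets a category 'Hepatic Event' with the rule "All PTs under SMQ (hepatic disorder"). It introduces this as an addition: "In addition, the following should have been included in the SAP". The only existing text that the note corrects is section 8.2.9.

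Three further sections depend on the definition. Section 8.2.8.1 starts from "A summary of liver-related TEAEs that are drug related". Section 8.2.8.2 does the same for serious liver-related events; its cross-references are to the definition of seriousness and to the table layout. Section 8.2.8.3 defines hepatotoxicity as AST or ALT of at least 3 x ULN "or at least one hepatic SAE (as described in §8.2.8").

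**The concern.** A word in the preferred term and a MedDRA grouping are different kinds of rule, and they select different events. Many liver events have coded terms that do not contain the word 'hepatic', so the rule in the outcome section is the narrower one. The SAP gives no order of precedence, and no note to file corrects section 2.3.2.8.

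At stake are three named secondary safety outcomes: liver-related TEAEs, those also related to study drug, and those that are serious. Section 8 plans no inferential tests for safety, so the tabulated counts are the whole result and the case definition determines them. Someone programming these tables could follow section 2.3.2.8 for one and section 8.2.8 for another, and report different liver counts without breaking any stated rule.

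**Working it through.** No sample size, power or error rate depends on this point, and the SAP states no figure to reproduce. The check compares the rules and then asks what the word rule would leave out.

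**Step 1. The rules side by side.**

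| Place | Rule | Type | Replaces another rule? |
|---|---|---|---|
| Section 2.3.2.8 | Preferred term specifies 'Hepatic' | Word in the term | No |
| Section 8.2.8 | Preferred terms under 'Hepatic disorders' in MedDRA | Grouping, level not named | No |
| Note to File 2 | All preferred terms under the hepatic disorder SMQ | Grouping, level named | No, added |

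There are three wordings. In substance there may be only two rules, because the grouping in section 8.2.8 may be the same SMQ that Note to File 2 names. The SAP does not say so. Section 2.3.2.8 differs from both in either case.

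**Step 2. What the word rule leaves out.** The SAP lists no preferred terms, so the list here is an assumption: thirteen illustrative liver-event wordings, each searched for 'hepatic' without regard to case.

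- Not matched (10): ALT increased, AST increased, alanine aminotransferase increased, aspartate aminotransferase increased, transaminases increased, blood bilirubin increased, hepatitis, hepatitis B, hepatotoxicity, drug-induced liver injury.
- Matched (3): hepatic enzyme increased, hepatic function abnormal, hepatic failure.

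The split of 10 to 3 describes this list only. It does not estimate the share of events lost, which would need event frequencies that the SAP does not give. It does show that the loss would include hepatitis and hepatotoxicity and most, but not all, wordings for an enzyme rise.

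**Step 3. Which outputs are exposed.**

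- The outcomes in section 2.3.2.8 (liver-related, drug-related liver, serious liver) are exposed directly, because the word rule is their stated definition.
- The tables in 8.2.8.1 and 8.2.8.2 are subsections of 8.2.8, and the natural reading puts them under its grouping. Neither says so, and both report outcomes that section 2.3.2.8 defines by the word rule.
- The hepatic SAE in 8.2.8.3 cites section 8.2.8, so the word rule does not reach it. It does inherit the unnamed level of the grouping.
- AST and ALT rises are counted from laboratory results in 8.2.8.3 and Table 3, whatever the AE coding.

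**Step 4. Whether the laboratory route makes up the loss.** It does so for the occurrence of enzyme rises. It cannot do so for the drug-related and serious outcomes, because a laboratory value carries no investigator assessment of relatedness and no seriousness flag. Those two outcomes can come only from adverse-event records chosen by a liver-related definition.

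**The case against.** The strongest reply is that section 2.3.2.8 is an outline and section 8 is the specification. The opening of section 2.3 describes its subsections as outlining the outcomes; the operational rule is in 8.2.8, and the dependent tables sit beneath it. The sentence in 2.3.2.8 is loosely punctuated, and 'specifies' need not mean a literal text search. On that reading the tables use a MedDRA grouping, Note to File 2 adds the full SMQ, and nothing is under-counted.

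Much of this stands. Under-counting follows only if the word rule is applied, and applied literally. What does not stand is the idea that the conflict is therefore harmless: the outcome section gives its own rule, it disagrees with the table section, and the notes to file left it in place. Note to File 3 even rewrote a sentence on liver enzyme plots in section 8.2.8.2 without touching the definition.

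A reader might also infer more than the SAP supports:

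- *That the hepatotoxicity composite is distorted by the word rule.* It is not: it cites section 8.2.8, and its laboratory component needs no AE coding.
- *That all enzyme-rise events would be lost.* A term worded 'hepatic enzyme increased' would be kept.
- *That tables in the report are bound to disagree.* They agree if the tables follow section 8.2.8 and its grouping is the SMQ of Note to File 2.
- *That transaminase rises would go unseen.* Section 8.2.8.3, Table 3 and the liver enzyme plots all use laboratory results.
- *That the loss would differ between arms.* Section 2.3 describes one MedDRA coding process for all adverse events, and nothing suggests that it works differently by arm.

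**Conclusion.** The inconsistency is real and should be corrected. Section 2.3.2.8 defines a named safety outcome by a narrower rule than the section that tabulates it, and no text says which prevails. If the narrower rule were applied literally, the counts of liver-related, drug-related liver and serious liver TEAEs would be too low, because hepatitis, hepatotoxicity and most transaminase terms would not qualify.

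The size of any under-count cannot be computed. The conclusion rests on two assumptions: that 'specifies' is read as the word appearing in the term, and that the illustrative wordings resemble the terms actually coded. If section 8.2.8 was used throughout, nothing is lost through the word rule; what remains is contradictory wording and a grouping whose level is not named. No hypothesis test, power figure or efficacy conclusion is affected. The point is still more than editorial, because it decides which events count in outcomes that laboratory data cannot fully replace.

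**What to change.** Delete the word rule in section 2.3.2.8. Define 'liver-related' once, as all preferred terms in the hepatic disorder SMQ already planned in Note to File 2, and say explicitly whether that covers both narrow and broad terms. State that this definition governs sections 2.3.2.8, 8.2.8, 8.2.8.1 and 8.2.8.2 and the hepatic SAE in section 8.2.8.3. In section 8.2.8, replace 'Hepatic disorders' with the name of the SMQ so that the level is no longer open.

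The cost is a wording change, in the SAP or a further note to file. The SMQ search is already planned, so no new data or coding is needed. The downside is that liver-related counts may be higher than under the word rule.

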### **2.3.3. Clinical safety laboratory measurements**

The incidence of newly notable (an abnormality observed post baseline that meets the notable criteria) grade 3 or 4 severity for laboratory parameters according to DMID grading. Participants are considered to have notable laboratory abnormalities if his/her response falls within the specified definitions (see Table 3 in §8.3.1) at least once during the treatment period.

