### **3.8. Newly notable abnormalities**

A newly notable laboratory abnormality is defined as an abnormality observed post baseline that meets the notable criteria in [Table 3](#) and that did not exist at baseline. Participants can still meet the criteria for newly notable laboratory if the baseline value is missing.

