## **8.3. Clinical Evaluation**

### **8.3.1. Clinical Laboratory Evaluation**

A list of laboratory tests (haematology, clinical chemistry, and urinalysis) to be included in the analysis is presented in [§7.3 of the protocol](#). Laboratory assessments done by a central laboratory will be summarised in tables. All summaries will be based on the units provided by the central laboratory, no conversion will be done. The laboratory evaluations will be summarised for baseline, post-baseline, and change from baseline at week 8, end of treatment (week 17 or week 26), 52 week and 104 week FU.

Laboratory values outside normal ranges will be identified, and the number and percentage of participants with at least one post-baseline abnormality will be summarised in shift tables comparing the baseline results to each post-baseline timepoint for those participants with results at both timepoints.

The table below displays the general variables and thresholds of interest. Participants are considered to have notable laboratory abnormalities if his/her response falls within the specified definitions at least once during the treatment period.

Table 3:Notable Criteria for Laboratory Data

Lab Test Type	Laboratory Variable	SI Units
Liver	AST	>3 x ULN and ≤ 5 x ULN >5 x ULN and ≤ 8 x ULN >8 x ULN
	ALT	>3 x ULN and ≤ 5 x ULN >5 x ULN and ≤ 8 x ULN >8 x ULN
	Total Bilirubin	>2 x ULN
	Alkaline Phosphatase (ALP)	>2 x ULN
Chemistry Labs	Other: ALT or AST > 3 x ULN and total bilirubin > 2 x ULN ALT or AST > 3 x ULN and total bilirubin > 2 x ULN and ALP < 2 x ULN (potential Hy's law case)	
	Lipase	>2xULN to ≤5XULN >5xULN

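### The laboratory safety outcome has two conflicting definitions: DMID grade 3 or 4 in any laboratory parameter (§2.3.3), but 'notable' only by Table 3, which as shown covers liver tests and lipase in ULN multiples

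*SAP*

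**What the plan says.** SAP §2.3.3 (Clinical safety laboratory measurements) gives the outcome as the incidence of newly notable abnormalities of "grade 3 or 4 severity for laboratory parameters according to DMID grading". That sentence names no analytes. The next one says that a participant has a notable abnormality if a result meets the Table 3 definitions at least once during the treatment period.

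SAP §3.8 repeats the link: "A newly notable laboratory abnormality is defined as an abnormality observed post baseline that meets the notable criteria" of Table 3 and was not present at baseline. A missing baseline value does not prevent a result from counting.

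SAP §8.3.1 (Clinical Laboratory Evaluation) brings haematology, clinical chemistry and urinalysis into the analysis. For all of these it plans summaries at baseline, post-baseline and as change from baseline. It then adds a count against the reference range, shown in shift tables: "Laboratory values outside normal ranges will be identified". Table 3 is introduced separately: "The table below displays the general variables and thresholds of interest". Its last row, lipase, is cut at ">2xULN to ≤5XULN" and above 5 x ULN.

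SAP §3.7 gives a general safety rule. It includes a post-baseline abnormality if the criterion was not met at baseline, or if the toxicity grade has risen above the baseline grade.

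**The concern.** One outcome is tied to two rules that need not give the same count. A programmer who starts from the first sentence of §2.3.3 would grade every laboratory parameter by DMID and count grades 3 and 4. One who starts from §3.8 would count only Table 3 results. Both could say that they followed the SAP.

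The analytes outside Table 3 are where this matters most. Note to File 2 names myelosuppression as an event of interest, and §8.2.9 names myalgia. Both are summarised from adverse event terms. A laboratory value enters such a table only if someone reported it as an adverse event, and §1.2 says that participants and staff know the allocation. Central laboratory values, graded by a fixed rule, would be the objective cross-check. On the literal reading none is planned for blood counts or muscle enzymes.

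**Working it through.** No sample size, power, alpha or event figure is involved, and the SAP gives no figure to reproduce. The check is a side-by-side reading with a simple count.

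**1. Scope of the outcome.**
- §2.3.3, first sentence: laboratory parameters in general, DMID grade 3 or 4.
- §2.3.3, second sentence, and §3.8: only what meets Table 3.
- §8.3.1: the laboratory analysis covers haematology, chemistry and urinalysis.

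**2. Content of Table 3 as shown.**

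| Row | Limits (x ULN) | Number of limits | DMID grade stated |
|---|---|---|---|
| AST | >3 to ≤5; >5 to ≤8; >8 | 3 | none |
| ALT | >3 to ≤5; >5 to ≤8; >8 | 3 | none |
| Total bilirubin | >2 | 1 | none |
| ALP | >2 | 1 | none |
| Liver combinations | two composites of ALT or AST, bilirubin and (in one) ALP | 2 | none |
| Lipase | >2 to ≤5; >5 | 2 | none |

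Total: 3 + 3 + 1 + 1 + 2 + 2 = 12 limits on 5 distinct analytes. None states a DMID grade, and none concerns haematology or urinalysis.

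**3. Where a severe value outside Table 3 goes.** Take a blood count in the DMID grade 4 range.
- Outcome of §2.3.3 read through §3.8: not eligible, because Table 3 has no criterion for it.
- §8.3.1 by-visit summaries: included, as one value among many.
- §8.3.1 shift tables: included as out of range, not separated from a slight deviation.
- §8.2.2 table of grade 3 or 4 TEAEs, and the Note to File 2 table for haematopoietic cytopenias: included only if reported as an adverse event.

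No section specifies a table of laboratory values by DMID grade.

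**4. Baseline rule.** Take a participant whose value already meets the criterion at baseline at grade 3 and reaches grade 4 on treatment.
- §3.7: counted, because the grade is higher than at baseline.
- §3.8: not counted on its plain wording, because the abnormality existed at baseline.

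**5. Do later documents resolve it?** Note to File 3 selects participants for liver enzyme plots by toxicity grade 3 or higher for AST or ALT. It thus uses grades without linking them to the Table 3 bands. None of the three Notes to File changes §2.3.3, §3.8 or Table 3.

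**The case against.** The strongest reply is that the SAP clearly expects laboratory values to be graded. §3.7 takes the highest grade within a visit and compares grades with baseline, and Note to File 3 speaks of graded laboratory tests. A sensible programmer could therefore build the DMID table from the first sentence of §2.3.3, and treat Table 3 as an extra list of liver and lipase thresholds, which is a legitimate selection. This stands in part. It shows that the fault is a conflict between two rules, not a decision to ignore severe values. It does not remove the conflict, because §3.8 defines newly notable by Table 3 alone.

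A reader might infer three stronger things that the SAP does not support:

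- **That severe values in other analytes are never counted.** They are counted as out of range in the §8.3.1 shift tables and, if reported, in the TEAE and Note to File 2 tables. What is missing is their count as grade 3 or 4 in the laboratory outcome.
- **That the Table 3 bands cannot correspond to DMID grades 3 and 4.** The SAP gives no DMID limits, so this cannot be checked. Three AST or ALT bands could subdivide two grades. The limits may be in the protocol, and their absence here is no fault.
- **That the count for other analytes is zero whatever the data show.** That assumes Table 3 is complete. It was read from PDF and its layout is broken. The abbreviation list contains ANC, CPK, GGT, HGB, WBC and RBC, which the visible text never uses. Lost rows cannot be excluded; nor can leftovers from merging the efficacy and safety SAPs.

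**Conclusion.** The point holds as an internal contradiction in a secondary safety outcome. §2.3.3 promises DMID grade 3 or 4 across laboratory parameters. §2.3.3 and §3.8 together deliver Table 3, which as shown is 5 analytes and 2 liver composites in ULN multiples without grades. §3.7 and §3.8 also differ on a participant who worsens from an abnormal baseline.

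The consequence is limited. §2.3 and §8 make laboratory safety descriptive, so no test, error rate or efficacy conclusion is touched. The number of participants affected cannot be estimated from the SAP, and nothing in it shows that toxicity would be under-reported in one arm. That is a possibility in an open-label trial, not a finding.

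The analyte-coverage part rests on Table 3 being complete as read. If rows were lost, that part weakens or falls away. The absence of any link between grades and ULN bands in the visible rows would remain, and so would the difference between §3.7 and §3.8. The change is worth making because the outcome is ambiguous as written and the remedy is cheap.

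**What to change.** - **§8.3.1:** add one by-arm table of participants whose worst post-baseline value reaches DMID grade 3, and grade 4, for every DMID-graded haematology and chemistry analyte. Count a participant when the grade is higher than at baseline (the §3.7 rule). State the period covered (§2.3.3 uses the treatment period) and how a missing baseline is handled (§3.8 lets it count). Cite where the DMID limits are found.
- **Table 3:** keep it as a separate liver and lipase summary. Confirm against the source file that all its rows are present.
- **§2.3.3 and §3.8:** stop making the DMID grade 3 or 4 outcome depend on Table 3, and align the §3.8 baseline wording with §3.7.

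A smaller alternative is to reword §2.3.3 so that the outcome covers only the Table 3 criteria. That removes the contradiction in scope but leaves severe values in other analytes ungraded, and §3.7 and §3.8 would still have to be aligned.

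The cost is a few lines of SAP text, or a further note to file of the kind already used for other safety tables, and one descriptive table from laboratory data already collected.

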### **2.3.4. Electrocardiogram**

The electrocardiogram (ECG) results (heart rate, RR interval, PR interval, QRS interval, QT interval and QTc interval), which are read by a central cardiology service, observed measurements and change from baseline. QT/QTc intervals, maximum change from baseline, will be categorised according to §8.4 below. The ECG results will be considered at baseline, week 8, week 17, week 26, week 39 and early withdrawal in all participants.

